7.3.6 Serious Adverse Event Reporting and Follow-up

The Sponsor is required to inform worldwide regulatory authorities of SAEs that meet specific criteria and to do so in an expedited manner. Specifically, suspected, unexpected serious adverse reactions (SUSARs) are subject to expedited safety reporting requirements. The Sponsor will report SUSARs to the appropriate authorities within the timelines and format required by local regulations. The Sponsor will also inform all participating investigators of SUSARs and any new safety risks.

Therefore, study centers must report all SAEs, including death, due to any cause, that occur from the time the ICF is signed until the subject completes the last study visit or withdraws from the study, to the Sponsor or its designee within 24 hours of the study center staff learning of its occurrence. When reporting an SAE, all relevant seriousness criteria should be recorded, and relationship to study drug should be assigned at the time of initial report, as this is required to determine regulatory reporting.

The Investigator must also report applicable SAEs to the Institutional Review Board (IRB) / Independent Ethics Committees (IEC) according to the requirements of the IRB/IEC. The Sponsor will provide the Investigator with information on SUSARs from other study centers or other studies conducted with the study drug to provide to IRBs/IECs.

The Investigator is expected to institute appropriate diagnostic and therapeutic measures necessary to treat and promote resolution of the SAE. Any medications or procedures used to treat the SAE must be recorded on the appropriate pages of the subject's eCRF. The Investigator must determine whether the seriousness of the event warrants discontinuation of study drug.

The Investigator is expected to proactively follow up on the SAE with the subject at subsequent visits/contacts and to report follow-up information on the SAE to the Sponsor or its designee. All SAEs will be followed until no further medical intervention is warranted (eg, the event resolves, becomes medically stable, or is assessed as chronic) or until the subject is lost to follow-up.

The Sponsor or designee may contact the study center to solicit additional information or to follow up on the event. If requested, medical records (such as laboratory results, radiology reports, progress notes, hospital admission and emergency room notes, holding and observation notes, discharge summaries, autopsy reports, and death certificates) should be sent to the Sponsor or its designee after redacting all information that personally identifies the subject or hospital staff (per the European General Data Protection Regulation).

After a subject's last study visit, the Investigator is not obligated to actively seek AEs or SAEs. However, if the Investigator learns of any SAE, including a death, at any time after a subject has been discharged from the study, and he/she considers the event reasonably related to the study drug or to study participation, the Investigator must notify the Sponsor or designee within 24 hours of learning of the event.

7.3.7 Reporting of Pregnancy

Any pregnancy in a female subject or in the female partner of a male subject that occurs from the time the subject signs an ICF until a subject's last study visit must be reported to the Sponsor or its designee within 24 hours of study center staff learning of its occurrence. A pregnant female subject will be immediately discontinued from study drug.

The subject or pregnant partner should provide consent and then will be followed throughout the course of the pregnancy. Pregnancy follow-up information, including the status and health of the mother and the child and the outcome of the pregnancy, will be reported to the Sponsor or its designee. Any premature termination of the pregnancy will be reported. Any complication of the pregnancy affecting either the mother or the fetus that meets seriousness criteria will be reported as an SAE. A planned elective termination of the pregnancy will not be considered an SAE.

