4.4 Subject Early Termination

Subjects may choose to discontinue study drug or withdraw from study participation at any time, for any reason, specified or unspecified, without prejudice. The Investigator and/or Sponsor may also discontinue a subject's study drug or withdraw the subject from the study at any time. The

Investigator will discontinue a subject's study drug if the Investigator concludes that continuation would be detrimental to the subject's safety or well-being.

Reasons for premature discontinuation of study drug / withdrawal from the study may include:

- Pregnancy
- Adverse event
- Death
- Physician decision
- Subject decision
- Lack of efficacy
- Protocol violation
- Study termination by the Sponsor
- Lost to follow-up
- Other, to be specified

If ET occurs for any reason, the Investigator must make every effort to determine the primary reason for the ET and record this information on the eCRF. The Investigator will also schedule ET procedures for a subject who terminates early but does not withdraw consent for study participation (see [Section 8.11](#)). ET procedures consist of Visit 8 (Week 12), Visit 9 (Week 14), and Visit 10 (Week 24) (whichever visits the subject has yet to complete at the time of ET). Subjects who discontinue study drug as the result of an AE will also be followed according to [Section 7.3.4](#). Subjects who withdraw consent will be considered withdrawn from further study participation.

If a subject fails to appear for study visits without stating an intention to withdraw, the site must make every effort to regain contact with the subject, including making 3 telephone calls to the subject and, if necessary, sending a registered letter to the subject's last known mailing address. Attempts to contact the subject will be documented in the subject's site file. If the subject continues to be unreachable, the subject will be considered lost to follow-up and thus withdrawn from the study.

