5.3 Contraception Guidelines

Subjects must agree to adhere to the following contraception guidelines ([Heads of Medicines Agencies, 2014](#)) throughout the study and for 90 days after the last dose of study drug.

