8.6 Visit 6 (Week 8 ± 3 Days)

Set up the appropriate number of study drug vials to thaw in the refrigerator approximately 16 to 24 hours before scheduled study drug administration and according to [Section 6.1.2](#).

Complete the following procedures during the visit:

- Collect a urine sample for a urine pregnancy test for female subjects of childbearing potential and for urinalysis.
 - Any subject with a positive pregnancy test result must complete ET procedures and will be recorded as ET.
- Record any changes in concomitant medications since the previous visit.
- Record any new AEs that may have occurred since the previous visit and follow up on the status of any existing AEs.
- Obtain weight.
- Measure vital signs (blood pressure, heart rate, temperature, and respiratory rate) with subject in a sitting position after having rested for 5 minutes.
- Collect blood samples for clinical laboratory tests (chemistry and hematology).
- Collect pre-dose blood samples for serum PK and CSF1 (and anti-AMB-05X antibody, if the subject will be receiving the last dose of study drug at this visit).
- Optional assessment: If the subject will be receiving the **last** dose of study drug at this visit, collect pre-dose synovial fluid for PK, CSF1, and anti-AMB-05X antibody.
- Administer study drug via IV infusion to the affected joint.
- Collect post-dose blood samples for serum PK and CSF1 within 15 minutes after the end of infusion.
- Monitor the subject for at least 60 minutes post-dose for any adverse reactions, including any infusion-site reactions.
- Schedule the next visit with the subject.
- Contact IWRs to record the visit.

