8.7 Visit 7 (Week 10 ± 3 Days)

If the subject is on an every-2-weeks study drug regimen, set up the appropriate number of study drug vials to thaw in the refrigerator approximately 16 to 24 hours before scheduled study drug administration and according to [Section 6.1.2](#).

For all subjects, complete the following procedures during the visit:

- Record any changes in concomitant medications since the previous visit.
- Record any new AEs that may have occurred since the previous visit and follow up on the status of any existing AEs.
- Obtain weight.
- Measure vital signs (blood pressure, heart rate, temperature, and respiratory rate) with subject in a sitting position after having rested for 5 minutes.
- Collect a urine sample for urinalysis.
- Collect blood samples for clinical laboratory tests (chemistry and hematology).
- Collect blood samples for serum PK and CSF1 (before study drug administration, if applicable for the subject).
- Schedule the next visit with the subject.
- Contact IWRS to record the visit.

If the subject is on an every-2-weeks study drug regimen (and thus will be receiving the **last** dose of study drug at this visit):

- Collect a pre-dose blood sample for serum anti-AMB-05X antibody.
- Optional assessment: collect synovial fluid for PK, CSF1, and anti-AMB-05X antibody.
- Administer study drug via IV infusion.
- Collect post-dose blood samples for serum PK and CSF1 within 15 minutes after the end of infusion.
- Monitor the subject for at least 60 minutes post-dose for any adverse reactions, including any infusion-site reactions.

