8.10 Follow-up Visit 10 (Week 24 ± 7 Days)

- Record any changes in concomitant medications since the previous visit.
- Record any new AEs that may have occurred since the previous visit and follow up on the status of any existing AEs.
- Obtain weight.
- Measure vital signs (blood pressure, heart rate, temperature, and respiratory rate) with the subject in a sitting position after having rested for 5 minutes.
- Conduct a full physical examination and document any changes since the previous visit.

- Evaluate ROM of the affected joint.
- Administer the following PRO instruments:
 - PROMIS Physical Function Scale
 - Worst Stiffness NRS
 - BPI Short Form
 - EQ-5D-5L
- Collect a urine sample for a urine pregnancy test for female subjects of childbearing potential and for urinalysis.
- Collect blood samples for clinical laboratory tests (chemistry and hematology).
- Collect blood samples for serum PK and CSF1.
- Perform MRI. A central radiologist will evaluate MRI scans to assess tumors.
- Contact IWRS to record the visit.

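### Pregnancy reporting stops at the last study visit while required contraception runs to 90 days after the last dose, leaving up to 90 days unreported for subjects who withdraw consent, are lost, or miss the remaining visits

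*Combined protocol and SAP*

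**What the plan says.** - **Reporting.** Section 7.3.7 covers "Any pregnancy in a female subject or in the female partner of a male subject that occurs from the time the subject signs an ICF" and ends at the subject's "last study visit must be reported to the Sponsor or its designee within 24 hours of study center staff learning of its occurrence". It mentions neither the last dose nor 90 days. It is also the only section that asks for follow-up of mother, child and outcome, and it makes that follow-up depend on consent from the subject or partner.
- **Contraception.** Section 5.3 binds female and male subjects "throughout the study and for 90 days after the last dose of study drug".
- **Early termination.** Under Sections 4.4 and 8.11, a subject who terminates early without withdrawing consent is asked to complete whichever of Visits 8, 9 and 10 remain. Section 4.4 applies this whatever the reason for termination. It then adds: "Subjects who withdraw consent will be considered withdrawn from further study participation". Subjects who cannot be reached are also treated as withdrawn.
- **After discharge.** Section 7.3.6 keeps one duty alive: "However, if the Investigator learns of any SAE, including a death, at any time after a subject has been discharged from the study", and considers it reasonably related to study drug or participation, the sponsor must be told within 24 hours. Pregnancy is not named there. It is not a seriousness criterion in Section 7.3.2 either, although a congenital anomaly is.

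**The concern.** The protocol sets a period after the last dose in which conception is to be avoided, yet its duty to report a conception is tied to visit attendance. If a subject's last visit falls well before the 90 days are over, a pregnancy that begins in the remainder falls under no reporting or follow-up rule, even if the site hears of it.

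Section 10.1.3 requires that women be told the drug may carry unknown risks to a fetus, and that men be told of potential risk to a partner's fetus. With up to approximately 48 subjects planned, each pregnancy within the 90 days would be scarce safety information. No endpoint, sample size or analysis depends on it.

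**Working it through.** The protocol gives no derived figure here, so there is nothing to reproduce. The check compares day counts.

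**Inputs** (Schedule of Events, Section 1.3; visit sections 8.6 to 8.10):
- Last dose, every 2 weeks: Week 10, Day 71 ± 3
- Last dose, every 4 weeks: Week 8, Day 57 ± 3
- Visit 8: Week 12, Day 85. Visit 9: Week 14, Day 99
- Visit 10: Week 24, Day 169 ± 7, so Day 162 at the earliest
- Contraception period: 90 days after the last dose (Section 5.3)

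**1. Completers.** Days covered after the last dose = Visit 10 day − last-dose day.
- Every 2 weeks, nominal: 169 − 71 = 98. Shortest: 162 − 74 = 88, which is 2 days short of 90. Equivalently, 74 + 90 = Day 164 against Day 162.
- Every 4 weeks, nominal: 169 − 57 = 112. Shortest: 162 − 60 = 102. No gap.

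**2. Early terminators who keep consent and attend Visit 10 at Week 24.** An earlier last dose only lengthens the coverage. It runs nominally from 169 − 71 = 98 days (last dose at Week 10) to 169 − 1 = 168 days (only the Day 1 dose given). The only shortfall is the same 2-day extreme.

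This assumes that Visit 10 stays at Week 24. The text gives week numbers and does not say that the visits are re-timed. If they were re-timed from the early-termination visit at nominal spacing, coverage would be (169 − 85) = 84 days plus the days from last dose to that visit, so at most 90 − 84 = 6 days short.

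**3. Subjects who withdraw consent, are lost, or do not attend the remaining visits.** Uncovered days = 90 − (last attended visit day − last-dose day). The Week 12 and Week 14 rows assume that the full course of doses was given.

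| Last attended visit | Every 2 weeks | Every 4 weeks |
|---|---|---|
| The last-dose visit | 90 − 0 = 90 | 90 − 0 = 90 |
| Week 12 | 90 − (85 − 71) = 76 | 90 − (85 − 57) = 62 |
| Week 14 | 90 − (99 − 71) = 62 | 90 − (99 − 57) = 48 |

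**4. Does another section close the gap?** Section 7.3.6 reaches a birth defect or a serious complication learned of after discharge, if judged related. It does not reach an uncomplicated pregnancy, or a serious outcome judged unrelated.

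**The case against.** The case against is substantial and narrows the point.

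- **Most early leavers are covered.** Anyone who stops treatment but keeps consent is asked to attend through Visit 10, and Visits 8, 9 and 10 each include a pregnancy test for women of childbearing potential. This stands. It confines the material gap to the third group in the working.
- **Pregnancies found late are not lost.** Section 7.3.7 turns on when the pregnancy occurs, and its 24-hour clock starts when staff learn of it. On the natural reading, a pregnancy that began before the last visit but was discovered afterwards is still reportable. This stands. The gap concerns pregnancies that begin after the last visit.
- **Ninety days is a contraception rule.** Section 5.3 does not call it an exposure or risk period, so the two sections differ without strictly contradicting each other. This is fair. It is still the only figure the protocol gives for how long conception matters after dosing.
- **The yield is low.** The affected subjects are those the site no longer sees. This also stands, though a former subject or partner may contact the site, and the present text then requires nothing.

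A reader might go further and infer two things that the documents do not support:

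- *That subjects stopped for toxicity have the least coverage.* Section 4.4 schedules them for the same visits unless they withdraw consent, and adds adverse-event follow-up under Section 7.3.4. Nothing shows that those who withdraw or are lost are mainly toxicity cases.
- *That termination of the study by the sponsor would leave every subject on treatment uncovered.* Section 4.4 lists this among the reasons for early termination, so the remaining visits apply on its face, and Section 10.1.7 promises guidance on safe withdrawal. Neither section guarantees that Visit 10 would be held, so a gap is possible but not established.

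**Conclusion.** The mismatch between Sections 7.3.7 and 5.3 is real, and no other section closes it. It matters for a small, definable group: subjects who withdraw consent, are lost to follow-up, or do not attend the visits still due. The duty to report and follow a new pregnancy lapses for them while up to 90 days of the contraception period remain. For completers, and for early terminators who attend Visit 10, the shortfall is at most 2 days, and it needs a last every-2-weeks dose three days late together with Visit 10 seven days early.

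The conclusion rests on reading the last study visit as the last one attended, and on Visit 10 staying at Week 24 for early terminators. How many subjects will fall in the affected group cannot be estimated from the protocol. This is a minor point of safety reporting.

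**What to change.** In Section 7.3.7, change the end of the reporting period from the subject's last study visit to the later of the last study visit or 90 days after the last dose of study drug. State that it applies to any pregnancy the site learns of, including after early withdrawal, and that follow-up remains subject to the consent this section already requires.

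This uses the protocol's own figure and brings the uncovered time to 0 days for every subject, however the early-termination visits are timed. It changes no dose, visit, test or contraception rule. The cost is one phrase, one clarifying sentence and perhaps a few added reports. The limit is that no active contact is added, so only pregnancies that come to the site's notice will be captured.

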7.3.8 Clinically Significant Adverse Events

Clinically significant AEs include DLTs, AEs leading to discontinuation, and AESIs, all considered at least possibly related to study drug. The DMC will pay special attention to the occurrence of clinically significant AEs in their recommendations regarding continuation or suspension of dosing or enrollment, cohort expansion, initiation of a new dose cohort, and dose selection.

7.3.8.1 Dose-Limiting Toxicity

A DLT is defined as any Grade 3 or higher AE or SAE considered at least possibly related to study drug. For subjects who experience a DLT, the Investigator may exercise his/her clinical judgment and consider a reduction in an individual subject's maintenance dose (eg, from

2 mg/kg to 1 mg/kg, 4 mg/kg to 2 mg/kg, or 8 mg/kg to 4 mg/kg). Before implementing a dose reduction for a subject, the Investigator should contact the Medical Monitor to discuss the case. Subjects who are unable to tolerate the lowest dose level specified in [Section 4.1.2](#) will have study drug discontinued.

7.3.8.2 *Adverse Events of Special Interest*

AESIs for this study will include the following:

- Any events of liver toxicity, including elevations in liver enzymes (ALP, ALT, AST, bilirubin)
- Any periorbital edema or facial edema
- Grade 2 or higher: infections, nausea, vomiting, diarrhea
- Any infusion reactions
- Any neutropenia, anemia, or thrombocytopenia

All AESIs will be captured on an AESI report form. The DMC will pay special attention to AESIs considered at least possibly related to study drug.

7.4 Efficacy Assessments

Efficacy will be evaluated using the following assessments:

- MRI and central radiologist assessment of tumors based on RECIST v1.1 and TVS
- Clinician evaluation of ROM in the affected joint
- PRO instruments of PROMIS Physical Function Scale, Worst Stiffness NRS, BPI Short Form (including the Worst Pain NRS item), and EQ-5D-5L

7.4.1 Tumor Assessments

7.4.1.1 *MRI*

MRI procedures will be detailed in a separate MRI manual. MRI scans will be evaluated centrally by an independent radiologist blinded to a subject's dose. MRI scans will be assessed for tumor response based on RECIST v1.1 ([Section 7.4.1.2](#)) and based on TVS ([Section 7.4.1.3](#)).

7.4.1.2 *Response Based on RECIST v1.1*

OR will be centrally assessed from MRI scans using RECIST v1.1 and will include CR and PR ([Eisenhauer, 2009](#)). A CR is defined as disappearance of all tumors. A PR is defined as at least a 30% decrease in the sum of diameters of target tumors from the baseline sum of diameters.

7.4.1.3 *Response Based on Tumor Volume Score*

Quantification of tumor volume in TGCT is complicated by the irregular shape of the tumor and heterogeneous contrast between the tumor and its surrounding structures, which make it challenging to delineate tumor boundaries. TVS is a semi-quantitative scoring method for MRIs developed specifically for assessing TGCT ([Tap, 2015](#)). TVS draws from existing MRI scoring methods commonly used in arthritis (the Rheumatoid Arthritis MRI Score and the Whole Organ MRI Score) and from existing radiological experience in assessing changes in tumor volume and

patterns of distension of synovial cavities. TVS calculates tumor volume as a percentage of the estimated volume of the maximally distended synovial cavity or tendon sheath and provides a score in 10% increments. A score of 0 indicates no evidence of tumor; a score of 10 indicates a tumor that is equal in volume to that of a maximally distended synovial cavity or tendon sheath.

Tumor outcomes based on TVS will be classified according to the following:

- Complete response (CR): lesion is completely gone
- Partial response (PR): $\geq 50\%$ decrease in TVS relative to Baseline
- Progressive disease (PD): $\geq 30\%$ increase in TVS relative to the lowest score during the study
- Stable disease (SD): does not meet any of the other classifications

Tumor response based on TVS is defined as CR or PR. The overall number of responses and the number of subjects with and without disease progression will be assessed.

7.4.2 Joint Range of Motion

ROM of the affected joint will be assessed by qualified assessors at the study center and recorded in degrees. At Baseline, the plane of movement with the smallest (worst) relative ROM will be identified; only this plane will be used for evaluating change in ROM subsequently.

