2 INTRODUCTION

2.1 Tenosynovial Giant Cell Tumor

TGCT, also known as giant cell tumor of the tendon sheath (GCT-TS) or pigmented villonodular synovitis (PVNS), is a rare, locally aggressive and destructive mesenchymal neoplasm that arises in the synovium of joints, bursae, or tendon sheaths (de Saint Aubain Somerhausen, 2013; Staals, 2016).

TGCTs are caused by the excessive production of CSF1 resulting from genomic mutations (balanced translocations) at the CSF1 gene locus of chromosome 1p13 (West, 2006; Cupp, 2007). CSF1 acts at the CSF1R, leading to the proliferation of synovial-like mononuclear cells and recruitment of multinucleate giant cells, foam cells, siderophages, and inflammatory cells, which compose the bulk of the neoplasm (West, 2006; Cupp, 2007; de Saint Aubain Somerhausen, 2013). Although TGCTs are nonmetastatic in nature, they can develop into locally destructive lesions that cause significant local tissue injury, loss of joint function, and impaired quality of life (West, 2006).

The annual incidence of TGCT is estimated to be approximately 43 cases per 1 million individuals (Ehrenstein, 2017; Mastboom, 2017), with approximately 40,000 new cases per year in the US and Europe combined. TGCT most commonly affects individuals between 20 to 50 years of age (Ostuni, 2015). Two TGCT subtypes have generally been recognized: localized (l-TGCT) and diffuse (d-TGCT). Approximately 10% of TGCT are classified as diffuse (Mastboom, 2017). Regardless of subtype, TGCT nearly always involves a single joint, with the knee being the most commonly affected (up to 66% to 80%), followed by the ankle, elbow, shoulder, wrist/hand, and hip (Murphy, 2008).

TGCT presents clinically as a joint swelling or a firm, slowly enlarging mass (Ostuni, 2015). As the disease advances, patients experience attacks of pain, swelling, loss of range of motion, hemorrhagic joint effusions, cartilage destruction, and bone erosion, leading to eventual loss of joint function, impaired quality of life, and severe morbidity (Giustini, 2018; Tap, 2019). Joint replacement or even amputation might be necessary in cases of persistent disease (Staals, 2016). While TGCT is not lethal, it is a serious, chronic, debilitating illness with long-term consequences for joint function and quality of life (Mastboom, 2017).

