3.2 Secondary Endpoints

3.2.1 Efficacy Secondary Endpoints

The following efficacy endpoints will be assessed at Week 12:

- Proportion of subjects who achieve an overall tumor response (OR, which includes both CR and PR) per RECIST v1.1 ([Eisenhauer, 2009](#))
- Proportion of subjects with overall response based on TVS, a TGCT-specific method that calculates tumor volume as a percentage of the estimated maximally distended synovial cavity
- Mean change from Baseline in ROM score
- Mean change from Baseline in the PROMIS Physical Function score
- Mean change from Baseline in Worst Stiffness NRS score
- Percentage of subjects who respond with a decrease of at least 30% in mean BPI score from Baseline
- Mean change from Baseline in BPI score
- Mean change from Baseline in Worst Pain NRS score
- Mean change from Baseline in EQ-5D-5L health assessment

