4 STUDY DESIGN

4.1 Overall Design

This is a Phase 2, open-label, multiple-dose, dose-escalation study with an adaptive design that will enroll up to approximately 48 subjects with TGCT for 12 weeks of open-label treatment with IV AMB-05X. There will be a screening period of up to 4 weeks, a treatment period of 12 weeks, and a post-treatment follow-up period of 12 weeks. Each subject will receive a dose of AMB-05X every 2 or 4 weeks, for a total of 6 or 3 doses over the 12-week treatment period.

A study schema is provided in [Section 1.2](#), and the Schedule of Events is provided in [Section 1.3](#).

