4.1.1 Study Visit Schedule

Study visits will occur at the following times:

- At Screening (Visit 1)
- During the Treatment Period:
 - At Baseline/Day 1 (Visit 2), within 4 weeks after Screening (subjects receive their first dose of AMB-05X)
 - At Week 2 (Visit 3), Week 4 (Visit 4), Week 6 (Visit 5), Week 8 (Visit 6), and Week 10 (Visit 7)
 - At Week 12 (Visit 8) (the end of the Treatment Period and timepoint for assessment of primary and secondary endpoints; no AMB-05X is administered)
- During the Follow-up Period:
 - At Week 14 (Visit 9) and Week 24 (Visit 10)

Refer to [Appendix 5](#) for potential changes to study conduct in the context of COVID-19 (coronavirus disease 2019).

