A Sponsor DMC composed of qualified medical/clinical representatives from the Sponsor will review the available safety, tolerability, PK, PD, and efficacy data on an ongoing basis and provide recommendations regarding appropriate next steps in study conduct. Study enrollment will begin with an initial 3 subjects in Cohort A. The DMC will begin to review study data after the first 3 subjects complete Week 6 and will continue to review data throughout the study (each time 3 additional subjects [from any cohort] complete Week 12). Whenever a new dose is instituted during the study, the DMC will again review the available data once 3 subjects have completed Week 6 at the new dose.

The DMC will pay special attention to any clinically significant AEs. Clinically significant AEs include DLTs, AEs leading to discontinuation, and AESIs, all considered at least possibly related to study drug. A DLT is defined as any Grade 3 or higher AE or SAE considered at least possibly related to study drug. AESIs are defined in [Section 7.3.8.2](#).

Based on the recommendations of the DMC, the Sponsor may implement any of the following decisions without a protocol amendment, in the manner of a 3+3 dose escalation study design:

- If none of the first 3 subjects of a cohort experiences a clinically significant AE after 12 weeks on study drug, the Sponsor may elect to begin enrollment of the next cohort.

- If exactly 1 subject among the first 3 subjects of a cohort experiences a clinically significant AE, an additional 3 subjects will be enrolled into that cohort. If only 1 of the 6 subjects experiences a clinically significant AE, the Sponsor may then elect to proceed with enrollment of the next cohort.
- If exactly 2 subjects among the first 3 subjects of a cohort experience a clinically significant AE, the Sponsor will suspend enrollment in that cohort, and the DMC will make recommendations on next steps, such as suspending further enrollment in that cohort, enrolling another 3 subjects into the cohort, or initiating another cohort at a lower dose.
- If exactly 2 subjects in a 6-subject cohort experience a clinically significant AE, the Sponsor may elect to enroll an additional 3 subjects into that cohort at the same dose. If no additional clinically significant AEs occur, the Sponsor may then elect to proceed with enrollment of the next cohort.

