8.1 Visit 1 / Screening

After the subject provides signed consent and HIPAA authorization (if applicable), complete the following procedures. If necessary, screening assessments may be performed at more than 1 visit during the 4-week screening period.

- Obtain a 6-digit Subject ID from IWRS.
- Collect demographic information and take medical history.
- Record all concomitant medications, including dose amount and dosing frequency, taken within 4 weeks before Screening.
- Obtain height and weight.
- Measure vital signs (blood pressure, heart rate, temperature, and respiratory rate) with subject in a sitting position after having rested for 5 minutes.
- Conduct a full physical examination.
- Perform a 12-lead ECG.
- Evaluate ROM of the affected joint.
- Administer the following PRO instruments:
 - PROMIS Physical Function Scale
 - Worst Stiffness NRS
 - BPI Short Form
 - EQ-5D-5L
- Collect a urine sample for urinalysis.
- Collect blood samples for HBV, HCV, HIV, TB (QuantiFERON), serum pregnancy test for females of childbearing potential, and clinical laboratory tests (chemistry and hematology).
- Perform MRI. A central radiologist will evaluate MRI scans to assess tumors.
- For subjects whose TGCT diagnosis has not been previously histologically confirmed, a tumor biopsy will be performed during the screening period after the central radiologist has reviewed the subject's screening MRI scan.
- Once test results are obtained, check inclusion/exclusion criteria.

Individuals who successfully complete screening procedures and meet all eligibility criteria will be notified and scheduled for Visit 2 (Baseline). The interval between Visit 1 (Screening) and Visit 2 (Baseline) should not exceed 4 weeks.

For any individual who does not meet eligibility criteria, capture screen failure information, contact IWRS to report screen failure status, and record any changes in concomitant medications and AEs since Screening.

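### Picking the worst ROM plane on the same reading that anchors the change biases the mean change upward where a joint has several planes; the Screening reading could do the picking

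*Combined protocol and SAP*

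**What the plan says.** Section 7.4.2 sets the rule for range of motion (ROM): "At Baseline, the plane of movement with the smallest (worst) relative ROM will be identified; only this plane will be used". The efficacy assessments in the synopsis carry the same rule. Section 3.2.1 lists "Mean change from Baseline in ROM score" among the secondary endpoints assessed at Week 12.

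Section 4.1.1 identifies Baseline with Visit 2: "At Baseline/Day 1 (Visit 2), within 4 weeks after Screening (subjects receive their first dose of AMB-05X". Section 8.2.1 lists one ROM evaluation among the pre-dose procedures of that visit and mentions no repeat or averaged reading. Section 8.1 schedules an earlier one at Screening ("Evaluate ROM of the affected joint"), up to 4 weeks before. The ROM endpoint gives that earlier reading no role.

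The design in Section 4.1 has no control group: "This is a Phase 2, open-label, multiple-dose, dose-escalation study with an adaptive design". Section 9.3.5 summarizes efficacy with 95% confidence intervals and allows exploratory tests at 0.05 without multiplicity adjustment.

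**The concern.** If one reading does both jobs, the plane is chosen partly because its reading happened to be low that day. That part of the deficit is not expected to recur at Week 12, so the chosen plane appears to improve even if nothing has changed. The effect needs two conditions: some reading error, and at least two planes to choose from. An untreated group measured under the same rule would show the same shift and allow it to be subtracted, but there is none here. At stake is the within-cohort and overall mean ROM change and its confidence interval, which a reader would naturally take as evidence of benefit.

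**Working it through.** **Inputs.** The selection rule (Section 7.4.2 and synopsis), the endpoint (3.2.1), Baseline at Visit 2 with one ROM evaluation (4.1.1, 8.2.1), a separate Screening evaluation (8.1) and no control arm (4.1) come from the documents. The documents do not give the number of candidate planes per joint, the reading error, the spread between planes, or the reference for relative ROM. They state no ROM figure, so there is none to reproduce. Everything numerical below rests on assumptions.

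**Model.** A joint has k candidate planes on a common relative scale. Plane j has true value m_j, which does not change. The Visit 2 reading is m_j + e_j and the Week 12 reading is m_j + f_j, with independent errors of mean 0 and SD s. J is the plane with the lowest Visit 2 reading. The expected apparent gain is E[f_J] − E[e_J] = −E[e_J].

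**Equal planes.** The gain is s × E(largest of k standard normals). For k = 1 it is 0. For k = 2 it is s/√π = 0.564s.

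**Two planes, one truly worse by d.** The gain is √2·s·φ(d/(√2·s)) = 0.564s × exp(−d²/(4s²)).
- d = 2s: 0.564 × 0.368 = 0.21s.
- d = 4s: 0.564 × 0.0183 = 0.01s.

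Simulation (400,000 draws per setting) agrees and extends this to more planes. Apparent gain in error SDs, with no true change:

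| Planes | All equal | One worse by 2 SD | One worse by 4 SD |
|---|---|---|---|
| 1 | 0 | – | – |
| 2 | 0.56 | 0.21 | 0.01 |
| 4 | 1.03 | 0.48 | 0.03 |
| 6 | 1.27 | 0.66 | 0.047 |

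If errors are shared across planes within a visit (correlation 0.5), the equal-plane values fall to 0.40, 0.73 and 0.90.

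**In degrees.** With assumed s of 3, 5 or 8 degrees and two equal planes, the gain is 0.564s = 1.7, 2.8 or 4.5 degrees.

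**Mix of joints.** Section 2.1 gives the knee as much as 66% to 80% of cases. Suppose the knee offers one candidate plane and all other joints four equal ones. The overall bias is then 0.34 × 1.03 = 0.35 or 0.20 × 1.03 = 0.21 error SDs. With two equal planes in the other joints it is 0.34 × 0.56 = 0.19 or 0.20 × 0.56 = 0.11.

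**Between cohorts.** With two cohorts of 12, all joints having four equal planes, the simulated difference is −0.002. If one cohort had four equal planes throughout and the other only one plane, it would be 1.03.

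**Separating the two steps.** If J is chosen on the Screening reading and its error is independent of the Visit 2 error, E[e_J] = 0; simulated gains are within 0.004. If those two errors have correlation ρ, a fraction ρ of the bias remains. At ρ = 0.5 that is 0.5 × 0.564 = 0.28 for two planes and 0.5 × 1.03 = 0.52 for four.

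**The case against.** The strongest objection is that the size is unknown and may be negligible. The rule looks for the most affected plane. If one plane is usually clearly worst, or the knee offers only one candidate, little bias is left. This stands.

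It is also fair to say that the same-reading premise is an inference. No section defines an analysis baseline, and the term is used loosely: tumor volume response is a "decrease in TVS relative to Baseline", yet the Schedule of Events has MRI at Screening and none at Visit 2. Section 9.3.1 promises a separate statistical analysis plan, which is not in the supplied text and might define the ROM baseline. Even so, Section 7.4.2 fixes the selection rule in the protocol itself, and nothing supplied separates the two steps.

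A reader might go further and infer that the bias steers dose decisions, since the monitoring committee will "review the available safety, tolerability, PK, PD, and efficacy data on an ongoing basis". The documents do not support that. The rule for moving to the next cohort refers to suboptimal exposure and efficacy in Section 4.1.2, and to exposure or efficacy in the synopsis. Those two wordings need reconciling, but neither gives ROM a threshold or weight.

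A reader might also infer a definite false-positive rate. With two equal planes and no mean effect, a two-sided 0.05 test rejects in about 12% of trials at n = 12 and 36% at n = 48 if individual true changes have SD 2s. If they do not vary, the figures are 28% and 84%. The spread comes from assumptions, testing is optional, and no ROM test is named, so these rates are illustrations only.

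**Conclusion.** The point holds in direction. Given at least two candidate planes, some reading error, and one Visit 2 reading doing both jobs, the within-cohort and overall mean ROM change is biased upward, with no control arm to remove the shift. The documents do not give its size. On the assumptions shown it is 0 with one plane, about 0.56 error SDs with two equally limited planes and 1.03 with four, and under 0.05 when one plane is worse by 4 SD. It largely cancels between cohorts with similar joints. The primary endpoint (treatment-emergent adverse events) and the 3+3 counts do not use ROM. A claim that the ROM result would be mostly artefact goes beyond the documents. This is a minor matter on a descriptive secondary endpoint, worth correcting because the correction is cheap.

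**What to change.** In Section 7.4.2 and in the matching item of the synopsis, state that the plane is identified from the Screening ROM reading (Section 8.1), and that the separate Visit 2 pre-dose reading of that plane (Section 8.2.1) is the ROM baseline. Both places must change, or the synopsis and body will disagree. No visit or procedure is added.

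Costs and limits:
- The reported gain may be smaller.
- The plane chosen at Screening may not be the worst one on Day 1.
- Screening may be up to 4 weeks before Baseline, while Section 5.1 requires a stable prescription analgesic regimen only for the 2 weeks before Baseline. The plane could therefore be chosen under a different regimen.
- Part of the bias remains if Screening and Visit 2 errors are correlated, about half at correlation 0.5.
- Bias from unblinded ROM assessors is not addressed; Section 6.3 blinds only the central radiologist.
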